## 6. Study Visits and Intermediate Contacts

Recalls for both groups will occur via phone questionnaire as well as follow-up visits. Participants will be contacted at 1 month, 2 months, 4.5 months and 9 months ( $\pm$  2 weeks) following restoration placement or application of SDF. Subjects will need to present to the clinic for follow-up visits at 3 months ( $\pm$  6 weeks), 6 months ( $\pm$  6 weeks), and for study completion at 12 months ( $\pm$  6 weeks) (Table 1). Subjects will also be called to schedule and confirm these follow-up visits; these short calls will require no payment to the study subjects. In the case of an emergency, an emergency visit will be scheduled at Mott Children's Health Center or the University of Michigan School of Dentistry. An emergency will be evaluated and treated according to the AAPD guidelines, followed by completion of appropriate case report forms (CRFs) and reporting to IRBs and study sponsors (Appendix 10, CRF 14-17). In the event of minor or major failure in either study group, the subject will be withdrawn from the study and teeth will be given the appropriate treatment as stated in the AAPD Guidelines free of charge, these teeth will be categorized as a failure, and a *CRF 04 Treatment Deviation CRF (Appendix 10, CRF 04)* will be completed.

**Table 1.** Patient Contact Interval

Patient Contact	Recall Interaction	Time Scale
Clinic Visit #1	Consent/Accent, baseline questionnaires, initial caries assessment, radiographs*, intervention	T = 0
Intermediate Contact	Attrition prevention, update contact information, follow-up on pain	T = 1 month, 2 months (Additional reminder for Clinical Visit #2)
Clinic Visit #2	Assessment for major and minor failure & assessment of pain and parent satisfaction	T = 3 months
Intermediate Contact	Attrition prevention, update contact information, follow-up on pain	T = 4.5 months (Additional call reminder for Clinical Visit #3)
Clinic Visit #3	Reapplication of SDF in that group; Assessment for major & minor failure, radiographs*, and assessment of pain and parent satisfaction	T = 6 months

Intermediate Contact	Attrition prevention, update contact information, follow-up on pain	T = 9 months (Additional call for scheduling/reminder for Clinical Visit #4)
Clinic Visit #4	Assessment for major & minor failure, radiographs*, and final questionnaires	T = 12 months

\* Radiographs will be obtained only if an existing radiograph within 30 days of the visit is not available.

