### 7.2. Clinical Variables

At the baseline visit the study teeth carious lesions will be assessed based on size (mm), dentin color (yellow, brown, black), dentin hardness (soft - any explorer penetration of dentin when very light force is applied or hard – no dentin penetration when using an explorer with very light force), and periapical radiographs (outer/middle/inner third of dentin, major/minor failure criteria). All information will be noted on the respective *CRF Intervention Visit* by the provider prior to treatment. These clinical characteristics will also be recorded for the SDF groups at follow-up visits (as the lesion is exposed clinically). Recall clinical visits will involve assessment of the lesion based on minor and major failure criteria (Table 2). All assessments will be noted on the respective *CRF 3 & 6 Month* (Appendix 10, CRF 10 & 11) or on the *CRF 12 Month* at the patient's 12 month recall (Appendix 10, CRF 12 & 13). Both groups will have periapical radiographs taken at the baseline and 6 and 12 month recalls (and at any other time if deemed clinically necessary). If a radiograph from within 30 days of the visit is available, a radiograph will not be taken at the study visit unless deemed clinically necessary. De-identified clinical photos will also be taken as deemed necessary for research and publication purposes, with parental consent. Length of time and cost for each intervention will be calculated and analyzed for comparison.

**Table 2.** Major and Minor Failure Criteria

	SDF Application	Conventional Restoration
Success	
 
• Caries arrested – dentin feels hard to explorer
 
• No clinical signs or symptoms of pulpal pathology
 
• Tooth exfoliated without major or minor failure
 
	
 
• Restoration appears satisfactory
 
• No clinical signs or symptoms of pulpal pathology
 
• Tooth exfoliated without major or minor failure
 

Minor Failure	
 
• Caries progression – soft dentin, increase in lesion size clinically or radiographically
 
• Reversible pulpitis to be treated without pulpotomy or extraction
 
	
 
• Secondary caries
 
• Restoration fracture or wear requiring repair
 
• Loss of restoration
 
• Reversible pulpitis to be treated without pulpotomy or extraction
 

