## **10. Statistical Analysis**

Power of the study will be fixed at 80% ( $\beta=0.20$ ) just as was used in calculation for necessary sample size, with  $\alpha = 0.05$  as the significance level. Data will be entered into SPSS Statistics or

another secured data collection system and data will be analyzed. Information will be stored on a password protected computer using an encrypted file and will be maintained as confidential protected health information (PHI). Examiners will be trained at the start of the study and calibrated on the use of the ICDAS criteria, and on the clinical outcome variables using extracted teeth to determine intra and inter-examiner reliability (dentin color, dentin hardness, and lesion size in mm), which will be measured with kappa statistics. A Chi-square test will be applied to determine if there is a difference in distribution of variables such as age, gender, brushing habits, fluoride exposure, etc. Chi-square tests will also be used to determine differences in dropout rates, failure rates, patient satisfaction/acceptance, and overall cost. The primary outcome, the proportion of children reporting major failures during the 12 month follow up period, will be analyzed using a mixed model with a binomial error structure. We will also analyze minor failures in a similar manner. The dependent variables will be a binary indicator of major failure, with differences between study treatments fitted as fixed effects. Estimates of the relative risk of major failure in the two groups will be presented in the form of odds ratios and associated 95% confidence intervals. Within this framework we will be able to estimate:

1. The mean difference between groups at the end of the follow up period;
2. The mean difference between groups across the whole of the follow up period; and
3. The difference in the rate of change of the outcome across the follow up period

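### Withdrawal and re-treatment at the first minor failure ends follow-up before the primary outcome, major failure over 12 months, has been fully observed

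*Combined protocol and SAP*

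**What the plan says.** Section 6 sets one consequence for either grade of failure: "In the event of minor or major failure in either study group, the subject will be withdrawn from the study". The tooth is treated under the AAPD guidelines, a treatment-deviation form (CRF 04) is completed, and "these teeth will be categorized as a failure". The grade is not named at that point.

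Table 2 in Section 7.2 defines minor and major failure separately. For SDF, minor failure includes caries progression, described as "soft dentin, increase in lesion size clinically or radiographically". For conventional restorations it includes secondary caries, loss of the restoration and "Restoration fracture or wear requiring repair". Reversible pulpitis is a minor failure in both arms. Major failure means pulpitis needing pulpotomy or extraction, abscess, or an unrestorable tooth.

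Section 10 defines "The primary outcome, the proportion of children reporting major failures during the 12 month follow up period". It adds that "The dependent variables will be a binary indicator of major failure" and that "We will also analyze minor failures in a similar manner". One of its listed estimates is "The mean difference between groups at the end of the follow up period".

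Clinic visits fall at months 3, 6 and 12. Section 9 gives withdrawn children forms and a completion or disenrollment letter, but no outcome visits. Section 11 continues monitoring only for children who could not complete an intermediate recall visit and wish to stay in.

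**The concern.** The event that stops observation is the lesser grade of failure in the same tooth whose major failure is the primary outcome. Loss of follow-up is therefore tied to the outcome and cannot be treated as random. It falls on children who have already failed once.

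The triggers also differ by arm: soft dentin or a larger lesion for SDF; secondary caries, fracture or wear, or loss of the restoration for conventional care. The share of children cut off before a major failure could be seen may differ by arm for that reason alone.

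If these children score 0, a child observed for 3 months counts the same as one seen free of major failure at month 12. The month-12 contrast in Section 10 also has no record for them. A child already scored as a major failure does not need one for the cumulative outcome. Outcomes that were never collected cannot be recovered at the analysis stage.

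**Working it through.** **The texts side by side.** Section 6 ends participation at a minor failure. Section 10 needs to know whether a major failure occurs at any time in 12 months. For a child with a minor failure at month 3 or 6, the remaining 9 or 6 months are unobserved. Sections 9 and 11 do not fill the gap. Section 10 gives no rule for missing data, censoring or competing events.

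**The plan's own figure.** Inputs from Section 4.2: 29% and 63% failure at one year, alpha 0.05, power 80%. Two-sided testing is assumed. With pooled variance, n per arm = [1.960 × √(2 × 0.46 × 0.54) + 0.842 × √(0.29 × 0.71 + 0.63 × 0.37)]² / 0.34² = 32.5, rounded up to 33. That is 66 in total, within 2 of the stated 68. For attrition, 34/0.70 = 48.6, rounded up to 49 per arm, which gives the stated 98. The planned size is not in dispute.

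**How much the treatment of these children can matter.** This is an illustration. Let P be the any-failure rate (0.63 SDF, 0.29 conventional), m the share of failures first seen as minor, and e the share of those found before month 12. Neither m nor e is in the document. Take m = 0.7 in both arms.

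Observed major failures: 0.63 × 0.3 = 0.189 and 0.29 × 0.3 = 0.087.

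*Scored 0.* Odds = P(1−m) / [1 − P(1−m)]: 0.189/0.811 = 0.2330 and 0.087/0.913 = 0.0953. Odds ratio 2.45.

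*Early minor failures treated as missing.* A minor failure first seen at month 12 is fully observed and stays at 0. Odds = P(1−m) / [1 − P(1−m) − Pme].

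| Found before month 12 (e) | SDF odds | Conventional odds | Odds ratio | Children left of 34 per arm |
|---|---|---|---|---|
| none | 0.189/0.811 | 0.087/0.913 | 2.45 | 34 and 34 |
| half | 0.189/0.5905 | 0.087/0.8115 | 2.99 | 26.5 and 30.5 |
| all | 0.189/0.370 | 0.087/0.710 | 4.17 | 19.0 and 27.1 |

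The last row equals the any-failure odds ratio, (0.63/0.37)/(0.29/0.71) = 4.17, only because m is the same in both arms.

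**Sensitivity to m, scored 0.** With m = 0.5 in both arms the odds ratio is 2.71; with m = 0.9 it is 2.25. If m differs by arm, the result moves either way:
- m = 0.8 SDF, 0.6 conventional: 0.126 against 0.116, odds ratio 1.10.
- m = 0.6 SDF, 0.8 conventional: 0.252 against 0.058, odds ratio 5.47.

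None of this shows what re-treated teeth would have done without re-treatment.

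**The case against.** The strongest reply is that the scoring is not really open. Table 2 grades the two failures separately and Section 10 analyses them separately, so a minor failure is 0 on the major indicator. That much stands. A reader might infer that such a child could equally be scored 1, since the tooth is called a failure, but this would contradict both Table 2 and Section 10. What remains is that 0 is an observed value only if the child is seen to month 12, and Section 6 stops that.

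A reader might also infer that the withdrawal rule takes power from about 82%, at 34 per arm with 63% and 29%, down to about 23% with scoring 0 and m = 0.7. The document does not support this. The 29% is described as a combined rate, and the 63% is the complement of the 37% arrest at 12 months in Section 3.5. The planning rates therefore do not refer to major failure. Most of the gap would remain with full follow-up: if 10% of minor failures went on to major failure, the rates would be 0.63 × 0.37 = 23.3% and 0.29 × 0.37 = 10.7%, with power of about 28%. That is a separate sample-size matter.

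Section 4.4 says that a provider can withdraw a failing patient. This does not soften the rule, because a general permission can stand beside the specific requirement in Section 6.

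The Appendix 10 forms, including CRF 04, are not in the text available for review, so a scoring rule there cannot be excluded. It could not restore follow-up that Section 6 ends.

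Finally, outcomes after re-treatment mix the two treatments, and other estimands are defensible. That is a fair limit on the remedy. It does not justify leaving the outcome truncated.

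**Conclusion.** The point holds. Followed as written, Section 6 truncates the primary outcome of Section 10 in children with a minor failure before month 12, through a trigger that is related to the outcome and specific to the arm. This is more than a missing detail, because the data would not exist.

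The size and direction of any bias are unknown. With m = 0.7 in both arms, the odds ratio runs from 2.45 to 4.17 according to how early minor failures are handled and when they are found. With unequal minor shares and scoring 0, it was 1.10 in one example and 5.47 in the other. These values rest on assumed shares and on the any-failure planning rates. They show sensitivity and do not predict the result. A reader might infer that the rule favours one arm, but the document gives no minor/major split or timing from which to say so.

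**What to change.** **Sections 6 and 9.** Separate the end of assigned treatment from the end of outcome collection. Every randomised child who has not withdrawn consent keeps the planned outcome assessments to month 12, whatever care is given. The clinical content of visits after re-treatment, including SDF reapplication and radiographs, is for the sponsor to decide.

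**Section 10.** Define the primary outcome as any major failure of the study tooth by month 12, analysed by assigned arm, and state that it includes re-treatment. Give the indicator value for each child:
- 1 for any major failure by month 12, including one after a minor failure;
- 0 if observed to month 12 without one;
- missing if lost earlier without one, with a named method and a sensitivity analysis.

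**To reconcile separately.** Table 2 lists soft dentin as a minor failure and Section 6 withdraws for minor failure, while Section 5.2 and Table 1 plan a second SDF application at month 6. These must be reconciled on whether a lesion still soft at month 3 or 6 is withdrawn or stays in. That clinical choice is the sponsor's.

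**Cost.** The change needs a text amendment and further visits for children who fail early. Under Section 8, the fees still payable would be 10 + 70 + 10 + 80 = $170 after a month-3 failure and 10 + 80 = $90 after a month-6 failure, within the $300 per child already offered. Staff time and any added radiographs are not costed in the document. Because outcomes after re-treatment mix the two treatments, the change may not restore events or power.

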## **9. Withdrawal Procedures**

Subjects will have the right to withdraw at any time. Alternative conventional treatment can also be provided to the SDF group at any time, if it is believed by the provider to be in the patient's best interest. Reasoning will be recorded, as a preference for or against one treatment arm may provide further information as to public acceptance of a treatment, and these subjects will be withdrawn, *CRF 04 Treatment Deviation* (Appendix 10, CRF 04) and appropriate additional forms will be completed and the parent will receive a *Study Completion or Disenrollment Letter* (Appendix 11). Although no adverse events are expected *CRF 15 Unanticipated Problem & CRF 16 Adverse Event Logs* will be available if necessary (Appendix 10, CRF 15 & 16). In the event that the protocol is ever deviated from (ie. Missed recall or appropriate study procedure not completed) a *CRF 14 Protocol Deviation* (Appendix 10, CRF 14) will be completed.

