As with any treatment provided in children, especially those as young as two, it is possible that the children may be uncooperative for their appointments and that recall procedures cannot be performed. If a complete recall procedure cannot be fully completed, it is possible to simply complete the portions of the recall that are able to be completed safely. Children who cannot complete an intermediate clinical recall visit but still wish to remain in the study will be continued to be monitored until the final study visit, and the reason for failure to complete the recall will be noted.

Finally, given the socioeconomic status of these patients, it may be difficult for parents to miss work as well as arrange transportation to and from appointments. For this reason, it was determined that study participants will receive a study participant fee to help offset transportation costs and to hopefully additionally assist with any other oral health care needs of the patient's immediate family if necessary.

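### Section 6 withdraws a child at a minor failure, so observation of the primary outcome, major failure over 12 months, stops early

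*Combined protocol and SAP*

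**What the plan says.** Section 10 defines the primary outcome as "the proportion of children reporting major failures during the 12 month follow up period". It adds, of the lesser category, "We will also analyze minor failures in a similar manner". Among the quantities it promises are group differences at the end of follow-up and across it, and "The difference in the rate of change of the outcome across the follow up period".

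Section 6 sets the rule on failure: "In the event of minor or major failure in either study group, the subject will be withdrawn from the study". The tooth then receives guideline treatment free of charge, and "these teeth will be categorized as a failure". Section 4.4 is softer: when treatment is failing in either arm, the provider recommends more treatment and may withdraw the child. Section 9 adds "Alternative conventional treatment can also be provided to the SDF group at any time", and where that happens "these subjects will be withdrawn".

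The only provision for staying in after a setback is in section 11. Children who cannot complete an intermediate visit but wish to continue "will be continued to be monitored until the final study visit". Nothing comparable is written for a child with a minor failure.

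On the SDF lesion itself, section 4.3 requires a soft, active lesion at entry. Table 2 requires hard dentin for success and names soft dentin under caries progression, a minor failure, without a time point. Failure is assessed at 3, 6 and 12 months. Section 5.2 orders a second SDF application at 6 months, without condition, because it may raise the arrest rate.

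**The concern.** A trial with major failure over 12 months as its primary outcome needs major-failure status to 12 months in every randomised child, unless it deliberately targets something narrower and says so. Here a written rule ends observation at a different event. That event depends on treatment: Table 2 defines minor failure differently in each arm, and the planning failure rates in section 4.2 differ (63% for SDF, 29% for conventional care). If early stopping differs between arms and the analysis has no rule for it, the primary comparison depends on a coding choice made after the data are in.

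The SDF arm has a second difficulty. If persistent softness at 3 months is itself a minor failure, the lesions that the 6-month reapplication is meant to help are removed before they receive it.

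**Working it through.** **1. The plan's own figure.** Section 4.2 gives 34 per group for 29% against 63% failure, with 5% alpha and 80% power. A two-sided pooled-variance calculation without continuity correction gives 33 per group, and power at 34 per group is 0.818. For 30% attrition, 34 / (1 - 0.30) = 48.6, so 49 per arm and 98 in all, as stated. The withdrawal rule does not change this calculation.

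**2. Follow-up lost per child**, at nominal visit times:
- minor failure found at 3 months: (12 - 3) / 12 = 75%, or 9 months
- minor failure found at 6 months: (12 - 6) / 12 = 50%, or 6 months
- minor failure first found at 12 months: none

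**3. What the missing coding rule does.** In one arm, let n be the children randomised, w those withdrawn for a minor failure, M the major failures seen in the others, and m the major failures among the w after retreatment, which nobody records. Ignore other losses.
- Risk under the full strategy, including rescue: (M + m) / n
- Withdrawn children counted as free of major failure: M / n, which is too low by m / n
- Withdrawn children treated as missing: M / (n - w)

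The first quantity is a weighted average of M / (n - w) and m / w. The third is therefore too high if retreated children have fewer major failures than the others, and too low if they have more. The error in the between-arm comparison depends on m and w in each arm. The documents give neither, so its direction is open. Treating later visits as missing also relies on an assumption the described model does not address: the minor failure that causes the gap is not in the model for major failure.

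**4. The SDF lesion under each reading of Table 2.**
- Literal: soft dentin at a visit is a minor failure. A lesion soft at 3 months is withdrawn before reapplication, and one soft at 6 months is withdrawn at that visit. This conflicts with the unconditional second application in section 5.2.
- Progression only: a lesion that was soft at entry and has not worsened has not progressed. The child stays in, but the lesion is neither a success (hard dentin is required) nor a failure.

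Either way the table needs a rule for a soft, stable lesion at 3 or 6 months.

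**5. Why no count of affected children is given.** The documents contain no 3- or 6-month rate of soft lesions. The 12-month non-arrest rates are 100 - 37 = 63% with annual application and 100 - 53 = 47% with twice-yearly application (section 3.5). By 24 months they are 100 - 79.2 = 20.8% and 100 - 90.7 = 9.3%. Non-arrest falls with time. If that trend also holds before 12 months, more lesions would be soft at 3 or 6 months than at 12, so 47% to 63% is not an upper bound.

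**The case against.** The best defence has four parts.

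First, failure status is kept: the tooth is categorised as a failure and minor failures are analysed. This is true. What is lost is major failure after the minor one and, under the literal reading, the response to reapplication.

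Second, post-rescue status is needed only if the target is the treatment strategy including rescue. For failure under assigned care before rescue, stopping at the minor failure is coherent. This also stands, so a reader should not infer that the three section 10 estimates are impossible under any target. But section 10 does not name the narrower target, and its stated outcome covers the whole 12 months.

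Third, the literal reading of Table 2 is not the only one and may not be the intended one. Unchanged softness is hardly progression, and sections 4.2 and 5.2 both expect further applications to help. The 63% sizing rate does equate non-arrest with failure, but at 12 months, so it does not settle how softness is scored at 3 or 6 months. The visit workflows and case report forms are not in this copy and may settle it. For this reason the soft-lesion point is secondary. The main point rests on the explicit wording of section 6.

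Fourth, prompt free retreatment is good care. Agreed: the objection is to ending observation, not to treating the child.

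A reader might also infer that roughly half or more of the SDF arm would be gone by 6 months, from the 47% to 63% rates. Those are 12-month figures and give neither an estimate nor a bound for earlier visits. Nor does the at-any-time switch in section 9 show much asymmetry by itself: the other arm already receives conventional care, and sections 4.4 and 6 apply to both arms.

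**Conclusion.** The point holds in this form. In either arm, a stated rule ends observation of the primary outcome at a non-primary, treatment-dependent event, and the analysis section does not say how the child is then counted. The size that can be stated is per child: 9 of 12 months of major-failure observation lost at a 3-month minor failure, and 6 of 12 at a 6-month one. This rests on section 6 being applied as written, and on the available text, which describes no follow-up after withdrawal.

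The number of children affected, the direction of bias and the effect on the treatment estimate cannot be computed from the documents. It would go too far to say that the trial is biased for or against SDF. Major failures averted by retreatment are part of the effect if rescue belongs to the strategy, and are not bias. The sample size stands.

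The soft-lesion problem in Table 2 is a real but secondary ambiguity. Correcting both is a cheap improvement.

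**What to change.** - **Section 6:** replace withdrawal from the study at a minor failure with treatment as clinically needed, plus continued recording of major failure to 12 months at the visits already scheduled, subject to the family's right to withdraw. Align sections 4.4 and 9.
- **Scoring after retreatment:** use the major-failure criteria common to both columns of Table 2, namely pulpitis that needs a pulpotomy or extraction, an abscess, or a tooth that can no longer be restored. A restored SDF tooth can then be scored without choosing a column.
- **Section 10:** analyse all randomised children for major failure under the treatment strategy including rescue. Keep the first minor failure as its own outcome, do not code it as major, and state how a child lost after a minor failure is handled.
- **Table 2:** state that a soft, symptom-free, non-enlarging SDF lesion at 3 or 6 months does not by itself trigger withdrawal before the planned reapplication, and judge arrest at 12 months.

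**Cost.** No extra patients or visits. From section 8, the remaining payments after a 6-month failure are 10 + 80 = $90, and after a 3-month failure 10 + 70 + 10 + 80 = $170. Both lie inside the planned 50 + 4 x 10 + 210 = $300 per child. Small changes to the case report forms and to examiner calibration are needed. Some soft, symptom-free lesions would stay untreated longer, subject to the provider's freedom under section 9 to treat at any time.
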